pain, nausea, and range of motion¹⁵⁻¹⁷. The study found no increase in infection between control and treatment groups, but was underpowered to adequately assess this outcome. In 2013, Lunn *et al.* showed that perioperative IV steroids improved pain in forty-eight total hip arthroplasty patients¹⁸.

To date, the most comprehensive study on the use of IV steroids in total joint arthroplasty is a randomized controlled trial examining the effect of perioperative IV dexamethasone¹⁹. This study found significant reductions in anti-emetic and analgesic usage, superior VAS nausea and pain scores, and shorter length of stay compared to the control group. However, as this study investigated just one dosing regimen, the most efficacious dose and dosing regimen of perioperative dexamethasone is still unknown. Furthermore, this study had relatively short follow up, limiting its ability to determine the effect of IV steroids on long-term prosthetic knee function.

It is likely that orthopaedic surgeons are wary of perioperative steroid therapy due to concern of infection and wound healing disturbance. Certainly, these complications are devastating in the setting of arthroplasty. However, data from plastic surgery, general surgery, oral surgery, and orthopaedic surgery suggest no increase in wound complications from perioperative IV steroid administration⁴. Taken together, the literature has shown that low-dose, short-course IV corticosteroid regimens appear to be safe with regard to wound healing and infection. Nevertheless, no single study that is powered to adequately evaluate infection risk with steroid therapy in total knee arthroplasty currently exists, given the low baseline incidence of infection.

The proposed study seeks to comprehensively evaluate postoperative outcomes after total knee arthroplasty when using IV glucocorticoid therapy as part of a multi-modal pain control regimen. This prospective, randomized, placebo-controlled trial will build on previous studies by utilizing a superior study design with a larger sample size and evaluate a range of subjective and objective outcome measures with extended follow up of up to 1 year. More specifically, this study will assess the effect of different doses on key outcomes and also study the effect of perioperative dexamethasone on long-term knee function, considerations that have not yet been evaluated in the literature.

Objectives

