Our objective is to determine the effect of and compare two different doses of IV dexamethasone given preoperatively before TKA, when compared to placebo, using the outcome measures listed below:

Primary Outcome Measures

- To assess patient reported visual analog pain scores.
- To assess patient controlled analgesic usage.

Secondary Outcome Measures

1. To assess the soft tissue swelling about the operative knee after steroid administration.
2. To assess postoperative glucose levels after steroid administration.
3. To assess rehabilitation parameters such as postoperative knee range of motion and time to physical therapy clearance.
4. To assess incidence of nausea and vomiting postoperatively after steroid administration.
5. To assess patient satisfaction and function scores at 4 months with both Short Form (SF) – 12 and Knee Injury and Osteoarthritis Outcome Score Short Form (KOOS, Jr.) scores.
6. To assess hospital admission characteristics such as length of stay and rate of readmission.
7. To assess the risk of infection at 4 months and wound drainage at 7 days after perioperative steroid administration in total knee arthroplasty.

Study Design and Methods

We plan to conduct a prospective, double-blinded, randomized, placebo-controlled trial to evaluate perioperative glucocorticoid administration in total knee arthroplasty. There will be three arms in the study: 1) Placebo, 2) 10 mg dexamethasone, and 3) 20 mg dexamethasone.

Consent to Participation in the Study

Patients will be given the opportunity to participate in the study at the time of consent for surgery and blood product, which typically takes place in clinic during an evaluation for severe end-stage arthritis. It will be emphasized that study participation is optional, and that patients may be randomized to the control or placebo group. Patients will sign the combined informed consent and HIPAA form in order to participate in the study.

Method of Randomization

Once a patient chooses to be part of the study, he/she will be randomized in a blocked fashion to either the control group or to one of two intervention groups. Randomization will occur after informed consent has been obtained from the patients and after the preoperative screening examination is complete. Patients and investigators will be blinded to the randomization assignment. Emory's Investigational Drug Services will randomize each patient prior to dispensing the blinded dexamethasone/placebo doses.

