After the study is complete, statistical analysis will be performed using de-identified patient data to determine differences in primary and secondary outcomes. Repeated-measures analyses for VAS pain score (and change from baseline), knee ROM, functionality scores (SF-12 and KOOS, Jr.), and blood glucose will be done with a means model with SAS Proc Mixed (version 9, mixed linear models) providing separate estimates of the means by time on study (baseline, in hospital, day 7, and at 1,4 and 12 months after total knee arthroplasty) and treatment group (dexamethasone or control). A compound symmetry variance-covariance form among the repeated measurements will be assumed for each outcome and robust estimates of the standard errors of parameters will be used to perform statistical tests and construct 95% confidence intervals²⁶. T-tests will be used to compare the pairwise differences between the model-based treatment means (least-squares means) at each time point. Mean changes over time within a treatment group will be tested for linear trend. The model-based means are unbiased with unbalanced and missing data, so long as the missing data are non-informative (missing at random). A

dropout process is assumed to be missing at random if, conditional on the observed data, the dropout is independent of the unobserved measurements. Statistical tests will be two-sided. A p value < 0.05 will be considered statistically significant.

Adverse Event Reporting

At a six-month time point following initiation of the study, we will assess our results for any reportable adverse events, including postoperative infections. This data will be reported to the Emory Institutional Review Board (IRB). We will monitor for any adverse outcomes at each subsequent six-month interval.

Data Safety and Monitoring Plan

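### The secondary outcomes share the primary outcomes' p < 0.05 rule with no order, adjustment or exploratory label; the pairwise tests written for four of them already number 33

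*Combined protocol and SAP*

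**What the plan says.** The Objectives section lists two primary outcomes (VAS pain and analgesic use) and seven numbered secondary items, several of which hold more than one measure. The Statistical Analysis section treats both groups together: "statistical analysis will be performed using de-identified patient data to determine differences in primary and secondary outcomes". It names the outcomes that get a repeated-measures model. Besides VAS pain these are "knee ROM, functionality scores (SF-12 and KOOS, Jr.), and blood glucose will be done with a means model". For the modelled outcomes, "T-tests will be used to compare the pairwise differences between the model-based treatment means (least-squares means) at each time point". The section closes with "Statistical tests will be two-sided" and "A p value < 0.05 will be considered statistically significant".

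The design section states: "There will be three arms in the study: 1) Placebo, 2) 10 mg dexamethasone, and 3) 20 mg dexamethasone". The stated aim is comparative across doses: "Our objective is to determine the effect of and compare two different doses of IV dexamethasone given preoperatively before TKA". The Introduction adds that the trial will "also study the effect of perioperative dexamethasone on long-term knee function, considerations that have not yet been evaluated in the literature".

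Nowhere does the document rank the secondary outcomes among themselves, adjust for their number, require an overall test first, or call them exploratory. No test is named for swelling, nausea and vomiting, physical therapy clearance, length of stay, readmission, infection or wound drainage. The Data Safety and Monitoring Plan says only that a difference in infection risk between groups will be assessed.

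**The concern.** This is a stated rule, not a gap that a reader can fill charitably. Any pairwise difference between arms in ROM, SF-12, KOOS, Jr. or glucose, at any modelled time, may be called statistically significant if its own p value is below 0.05. That label is the same one the primary pain result would carry, and nothing makes it depend on the primary result. The trial could therefore miss on pain and still report a significant dose effect on, say, SF-12 at one visit, chosen from dozens of tests. Long-term function is the most exposed area, because the Introduction presents it as a new question while the sample size was set for VAS pain alone.

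**Working it through.** **The plan's own figure.** The document states no family-wise error rate, so there is none to reproduce. Its only design figure is for VAS pain: 47 per arm, and 3 x 47 = 141, which agrees with the stated total. The 47 itself cannot be confirmed because no SD is given. At 90% power, two-sided 0.05 and a difference of 1.5, it implies SD = 1.5 x sqrt(47 / (2 x (1.96 + 1.282)^2)) = 2.24. None of this sizing concerns the secondary outcomes.

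**Counting the tests.** Post-baseline times come from the Data Collection section and Table 1. None of the four measures is collected at day 7.

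- Knee ROM: in hospital, 1, 4 and 12 months = 4
- SF-12: 1, 4 and 12 months = 3
- KOOS, Jr.: 1, 4 and 12 months = 3
- Blood glucose: in hospital = 1

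Total 4 + 3 + 3 + 1 = 11 outcome-times. Three arms give 3 pairs, so 11 x 3 = 33 tests. The count is restrained: active and passive ROM, in flexion and extension, count as one outcome; all inpatient days count as one time; the tests of linear trend within arms are left out.

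**Expected false positives with no effect anywhere.** 33 x 0.05 = 1.65, whatever the correlation.

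**Chance of at least one.** If all 33 tests were independent it would be 1 - 0.95^33 = 82%. They are not: the three contrasts at one outcome-time share arms (three pairs on one outcome give 12.2%, not 1 - 0.95^3 = 14.3%), and outcomes correlate within patients. I therefore simulated equal arms under the null with a common correlation rho between outcome-times, took z = (difference of two arm means) / (its standard error) for each pair, and counted a trial as positive if any |z| > 1.96. For the two-group reading the single contrast is placebo against the average of the two dexamethasone arms.

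| Reading | rho 0 | 0.5 | 0.7 | 0.9 |
|---|---|---|---|---|
| 11 outcome-times x 3 pairs (33 tests) | 76% | 59% | 45% | 29% |
| One time for each of 4 measures x 3 pairs (12 tests) | 40% | 34% | 29% | 22% |
| 11 outcome-times, one two-group contrast (11 tests) | 43% | 30% | 22% | 13% |

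**Sensitivity.** Correlation within an outcome over time is likely to exceed correlation between different outcomes. In the 33-test case, 0.7 within and 0.2 between gives 63%; 0.7 and 0.5 gives 55%; 0.9 and 0.5 gives 47%. With 0.5 and 0.2 it rises to 69%. Steroids may truly change glucose, so a result there need not be false; dropping it leaves 30 tests and 56% at a common 0.5.

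**The case against.** Several points on the other side have force.

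*Not every secondary is covered.* A reader might infer that every secondary outcome is tested between all pairs of arms. The document does not say so. The pairwise rule is attached to the modelled outcomes, and the rest have no stated test. Counting all twelve or so named measures at three pairs each would add tests the plan does not specify, and would charge rare events such as infection and readmission a full 5% when their true error is probably lower. I have not relied on that count.

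*The model wording has two groups.* The Statistical Analysis section names the treatment factor with only two levels, dexamethasone and control. On that reading there is one contrast per time and the risk is 13% to 43%. The three-arm design, the objective of comparing doses and the very idea of pairwise differences all favour three levels, but the conflict is real and the document must resolve it.

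*The objectives are narrower than the model.* The function-score objective names 4 months. Restricting to ROM at four times and each score at 4 months (6 outcome-times, 18 tests) gives 54% at correlation 0 and 44% at 0.5. However, the analysis text does test the other visits.

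*Secondary outcomes are conventionally supportive.* The plan does separate primary from secondary, powers only pain, provides 95% confidence intervals, and uses mild verbs such as assess and study. That would suffice if the significance rule stopped at the primary outcomes. It does not, and convention does not override a written threshold.

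**Conclusion.** The point holds in this form. One unadjusted p < 0.05 rule covers primary and secondary outcomes, with no order and no exploratory label. For the four secondary measures with a written pairwise rule, the chance of at least one significant result under no effect is about 45% to 65% for most moderate correlations, a few points higher if different outcomes are only weakly related, and 29% to 76% over the whole range examined.

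A reader might go further and infer that a false secondary finding is more likely than not. The documents do not support that as a flat statement: it fails at a common correlation of 0.7 (45%), with one time per measure (22% to 40%), and on the two-group wording (13% to 43%). What does survive every reading is a risk well above 5%.

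The figures assume normal test statistics, equal arms and the stated correlations, none of which can be estimated from the documents. The consequence is for how secondary results may be described; the trial's validity and patient safety are not in question.

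**What to change.** In the Statistical Analysis section:

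1. Limit the p < 0.05 rule to the prespecified primary analysis of the primary outcomes.
2. State that secondary efficacy outcomes are exploratory, reported as estimates with 95% confidence intervals not adjusted for multiplicity, and with no claim of statistical significance.
3. Report glucose, infection and wound drainage as safety estimates with unadjusted confidence intervals, so that no signal is hidden by a correction.
4. State that the treatment factor has three levels, matching the design section.

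If the sponsor wants a confirmatory statement on function, one KOOS, Jr. contrast at 4 months could follow the primary test in a fixed sequence. That is optional and not yet possible: there are two primary outcomes and VAS is compared at several times, so a single primary contrast and time point would have to be named first.

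The four changes take a few sentences and need no new data or patients. The sponsor gives up confirmatory language for the secondary outcomes. The label does not supply the analysis methods missing for the unmodelled secondaries; those still have to be written.

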7. **Blood Glucose Levels:** The patient's blood glucose level will be recorded once preoperatively at the pre-anesthesia clinic visit several days before surgery, at POD 1 and at each subsequent in-hospital POD using a hemocue. These do not consist of extra blood tests, as blood draws at these time points are considered standard of care. This data is being collected because hyperglycemia is a potential complication of IV steroid use. If patients experience ketoacidosis or hyperglycemia greater than 300, the study drug/placebo will be discontinued.
8. **Functionality scores:** The Short Form (SF) – 12 and Knee Injury and Osteoarthritis Outcome Score Short Form (KOOS, Jr.) questionnaires will be administered to patients at the baseline visit and at each follow up clinic visit. Both of these standardized function questionnaires are well validated and widely accepted in the literature.
9. **Hospital length of stay and readmission:** We will record the length of each patient's hospital stay and any readmission to our hospital for the 12-month duration of study.
10. **Infection:** Patients will have standard follow up clinic appointments at 1 and 4 months after surgery, at which time the clinical presence of possible wound drainage and periprosthetic infection will be evaluated. Patients will be followed up to 1 year after surgery to monitor for latent infections.

Table 1: Outcome measure and data collection schedule

	Pre-operative clinic visit	Each inpatient day	7 day app usage	2 week app usage	1 month clinic visit	4 month clinic visit	12 month clinic visit
Consent, Enrollment, Randomization	X						
Pain assessment	X	X	X		X	X	X
Opioid usage		X					
Pain medication log			X	X			
Knee swelling	X	X			X	X	
Knee ROM	X	X			X	X	X
Physical therapy milestones		X					
Nausea/vomiting		X	X				
Blood glucose	X	X					
Postoperative infection/Wound drainage		X			X	X	X
Length of stay		X					
KOOS, Jr. and SF-12	X				X	X	X

Consent Process

Patients will be asked to participate in the study at a preoperative clinic visit. The risks, benefits and the optional nature of the study will be emphasized. Patients may withdraw from the study at any given time. Consent will be obtained from one or more of the following three people: the attending surgeon, the orthopaedic surgery resident, or the research coordinator.

Participant Selection

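### Glucose is collected to watch for hyperglycemia, but no count by arm of patients above the plan's own limit of 300 is prespecified; a small descriptive table would fill the gap

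*Combined protocol and SAP*

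**What the plan says.** Secondary outcome 2 under Objectives is "To assess postoperative glucose levels after steroid administration", with no threshold or incidence attached.

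Data Collection item 7 gives the reason for measuring it: "This data is being collected because hyperglycemia is a potential complication of IV steroid use". It schedules one preoperative reading and then readings "at POD 1 and at each subsequent in-hospital POD using a hemocue". It also contains the only glucose limit in the document: "If patients experience ketoacidosis or hyperglycemia greater than 300, the study drug/placebo will be discontinued". No unit is given for 300.

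The Statistical Analysis section covers glucose once, in the list of outcomes whose repeated-measures analysis "and blood glucose will be done with a means model with SAS Proc Mixed". The comparison is: "T-tests will be used to compare the pairwise differences between the model-based treatment means (least-squares means) at each time point". The group factor is written as "treatment group (dexamethasone or control", which has two levels although the trial has three arms.

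Adverse Event Reporting says that at six months "we will assess our results for any reportable adverse events, including postoperative infections", with further checks every six months. The Data Safety and Monitoring Plan states a comparison between groups for infection only. Other adverse outcomes go to the IRB as necessary.

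**The concern.** A complication happens to individual patients. The stated purpose of the glucose data is to watch for one, and the plan names a level at which it would act on a patient. The analysis, however, returns only arm means and differences between them. A reader of the results could learn that one arm's mean was higher, but not how many patients exceeded 300, how many had ketoacidosis, or how many had study drug stopped.

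This matters most for the dose comparison, which the Objectives make central. Two doses with similar mean glucose could differ in how many patients reach the limit, and the planned output would not show it. The two-level group factor adds to the problem: read literally, it may not separate 10 mg from 20 mg even for mean glucose.

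**Working it through.** **Inputs.** From the documents: 47 patients per arm (3 × 47 = 141), two-sided 0.05, and the limit of 300. The 47 was derived for pain scores. The documents give no glucose mean, SD or event rate, so there is no glucose figure to reproduce, and every glucose value below is an assumption for illustration.

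**1. Is a count planned anywhere?** The outcome list, item 7, the schedule in Table 1, the analysis section and both safety sections were read side by side. None defines a number or proportion above 300, a ketoacidosis count, a count of stopped study drug, or a highest value per patient, by arm. The safety sections name neither hyperglycemia nor, except for infection, a split by arm.

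**2. What a mean cannot show.** Suppose 3 of 47 patients are at 320 and the arm mean is 160. The other 44 must average (47 × 160 − 3 × 320) / 44 = 6,560 / 44 = 149.1. An arm with all 47 patients at 160 has the same mean. The first arm has three patients above the limit; the second has none.

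**3. Would the comparison of means miss such an arm?** Only under a narrow assumption. Take a placebo mean of 140, SD 25 to 35, 3 of 47 dexamethasone patients at about 320, and the other 44 raised by s. The mean difference is (3 × 180 + 44 × s) / 47. Power is from simulated Welch t-tests at 47 per arm on a single day, a simplification of the mixed model.

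| Rise s in the other 44 | Mean difference | Power, SD 35 to SD 25 |
|---|---|---|
| 0 | 540/47 = 11.5 | about 15% to 17% |
| 10 | 980/47 = 20.9 | about 62% to 83% |
| 20 | 1,420/47 = 30.2 | about 95% to over 99% |

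Low power requires that the drug leave 44 of 47 patients unchanged. With even a modest general rise, the means model would usually find a difference. It would still not report the three patients.

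**4. What a count would deliver.** Exact (Clopper-Pearson) 95% intervals:
- 0/47: upper limit 1 − 0.025^(1/47) = 7.5%
- 3/47 = 6.4%: 1.3% to 17.5%

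As a test the count is weak. By Fisher's exact test, 3/47 against 0/47 gives p = 0.24, 4/47 gives 0.12, and 6/47 is the first to fall below 0.05 (0.026). The chance of seeing at least one event in an arm is 1 − (1 − p)^47, which is 38%, 61%, 91% and 99% for assumed true rates of 1%, 2%, 5% and 10%.

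**5. What the readings can capture.** Under Therapeutic Intervention, the second and last dose follows the first by eight hours. Scheduled postoperative readings start on POD 1, so both doses may already have been given. A peak before that reading can be missed, and a stopping rule triggered by it may have no dose left to stop. Few recorded stops would therefore say little about how often the limit was crossed.

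**The case against.** The strongest case for the plan is that secondary outcome 2 is a continuous level, and a means model with robust standard errors suits it. The 300 rule governs when study drug stops and is not declared as an endpoint. Patients with diabetes are excluded (exclusion 14) and exposure is two doses, so values above 300 may be rare. A ketoacidosis case or a stopped dose could plausibly reach the general adverse-outcome reporting to the IRB. The count has little power, and readings from POD 1 may understate it, so a table showing 0/47 could reassure falsely.

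Most of this stands, and it rules out three stronger readings that a reader might infer:

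- That the plan would probably report no glucose difference while several patients crossed 300. This needs the rest of the arm not to move at all, which nothing in the documents supports.
- That such cases would never be reported. The general safety text could capture them; what is absent is a prespecified count by arm.
- That means are the wrong scale. They answer the outcome as worded, and a count complements them.

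The objection does not remove the gap. Notifying an IRB of single cases is not a comparison of arms, and no planned output relates individual patients to the one glucose limit the plan sets.

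**Conclusion.** The point holds as a reporting gap. Glucose is gathered with a complication in view, yet only means are prespecified, and no count by arm is planned for values above 300, ketoacidosis, or study drug stopped for either. This conclusion rests on the text alone and needs none of the assumed glucose values.

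Its size is modest. The gain is descriptive: at 47 per arm even zero events leaves rates up to 7.5% open, and the counts would rarely separate arms by a test. The documents give no rate for values above 300, so how often the table would show anything is unknown. It is a cheap improvement and does not put the planned analysis of secondary outcome 2 in doubt.

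**What to change.** Keep the means model for secondary outcome 2, with three arms in the group factor. Add to Statistical Analysis one descriptive table by arm (placebo, 10 mg, 20 mg), covering all dosed patients, including any later removed under exclusion 11 (transfer to ICU or another facility). It should give:

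- the number and percentage with any recorded postoperative glucose above 300, with ketoacidosis, and with study drug stopped for either, with exact 95% confidence intervals;
- the differences for each dose against placebo and for 20 mg against 10 mg;
- each patient's highest recorded inpatient glucose, summarised by median and range.

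The text should call these results descriptive, state the unit for 300, and say that scheduled readings begin on POD 1 and may miss earlier peaks. The sampling times and discontinuation rule in Data Collection item 7 must be reconciled with the dose timing under Therapeutic Intervention; which of them should change is a clinical matter for the investigators.

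The cost is a few lines of text and one table, using readings and safety information the plan already gathers, with no extra patients or blood draws. The drawbacks are wide intervals and the risk that zero counts are over-read, which the statement about timing is meant to limit.

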
Data Collection

Data will be collected by a number of different health professionals during enrollment, during the patient's postoperative hospital stay, by smart device application (app), and during the patient's routine postoperative follow up visits (1 month, 4 months, and 12 months). After surgery, no participants in any group will be subjected to any extra invasive tests or interventions related to their involvement in the study. Patients will not be informed whether or not they have received the study

drug until after all data collection is complete. The schedule of study activities and data collection are shown in Table 1.

1. **Pain assessment:** Postoperative pain will be assessed using the well-standardized and accepted visual analog pain scale. This data will be recorded at baseline, during the hospital stay, and at all follow-up visits. A smart device app will be used to record this information for the 7-day postoperative period. Questions will be asked morning, afternoon, and evening for every patient. Patients enter alarms for morning, afternoon, and evening the first time they use the app. Patients can later adjust these alarms if necessary. Timestamps will be recorded for each of these entries as patients will be asked about their 'average' pain over the preceding 4 hours, and they will be able to edit/modify prior entries at any time. Patients will also be asked during the first entry for the day if they were awoken from pain or nausea during the previous night, and if they click yes, they will be prompted to select pain scores corresponding to this event. There will be a comments section to provide patients the ability to enter text. Furthermore, during the hospital stay this data will be recorded with each vital sign assessment by the nursing per standard of care. The following scale will be used to assess pain:

[figure not shown]
©1983 Wong-Baker FACES® Foundation. www.WongBakerFACES.org
Used with permission.

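### The per-time treatment contrasts make no estimated adjustment for baseline, which costs some precision but causes no bias, and the role of VAS change from baseline is left open

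*Combined protocol and SAP*

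**What the plan says.** All of the modelling text is in the Statistical Analysis section. The outcomes are listed as "Repeated-measures analyses for VAS pain score (and change from baseline), knee ROM, functionality scores (SF-12 and KOOS, Jr.), and blood glucose". The model gives "separate estimates of the means by time on study (baseline, in hospital, day 7, and at 1,4 and 12 months" after surgery, by treatment group. Arms are then compared as follows: "T-tests will be used to compare the pairwise differences between the model-based treatment means (least-squares means) at each time point". A further test concerns time within an arm, not treatment: "Mean changes over time within a treatment group will be tested for linear trend". On covariance: "A compound symmetry variance-covariance form among the repeated measurements will be assumed for each outcome", with robust standard errors. Tests are two-sided at 0.05.

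The baseline values exist. For pain, the Data Collection section says "This data will be recorded at baseline, during the hospital stay, and at all follow-up visits". Table 1 also schedules preoperative ROM, SF-12, KOOS, Jr. and glucose.

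The primary outcome list names VAS pain scores without saying raw or change. The sample size is set on a VAS mean difference of 1.5 points between adjacent arms (3 between placebo and high dose), with 90% power and 47 patients per arm. No SD is given.

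**The concern.** A repeated-measures model that includes baseline can look as if it adjusts for baseline. This one does not, because every arm has its own free mean at every time, baseline included. A chance difference between arms at baseline is estimated and then left alone. The trial collects a baseline value for each of these outcomes and makes no use of it to sharpen the treatment contrasts.

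VAS is also to be analysed as change from baseline. That does use baseline, but with a weight fixed at 1 whatever the data show. When baseline predicts follow-up poorly, subtracting it adds noise. The text does not say what part the change analysis plays in the conclusion on pain.

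**Working it through.** **Inputs.** From the Statistical Analysis section: difference 1.5 (or 3), 47 per arm, 90% power, two-sided 0.05. Not in the documents, so assumed and varied: the follow-up SD; r, the correlation of baseline with follow-up; and k, the baseline SD divided by the follow-up SD.

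**The plan's figure.** The 47 can only be back-solved. With n = 2·SD²·(1.960 + 1.282)²/1.5², an SD of 2.24 gives 2 × 5.018 × 10.51/2.25 = 46.9, so 47. By the noncentral t the matching SD is 2.22 (1.5/2.22 = 0.676 SD), used below. If the plan used an omnibus F test on means 0, 1.5 and 3, the implied SD is 4.04; with three Bonferroni-corrected pairwise tests it is 1.98.

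**What the planned contrasts estimate.** With complete data and a free mean per arm and time, the generalised least-squares estimate within an arm is (nV⁻¹)⁻¹V⁻¹Σy, which is the raw mean vector. V cancels, so no compound symmetry correlation brings baseline in. A numerical fit agreed to about 10⁻¹⁵. With missing follow-up, the fitted correlation borrows a little from baseline: in one simulated arm with 15% missing, means moved by 0 to 0.05 SD. That does not adjust the contrast for baseline imbalance.

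**Variance relative to raw.**
- Raw: 1.
- Change: 1 + k² − 2rk, which is below 1 only if r > k/2.
- Baseline as covariate: 1 − r², for any k.
- Change minus covariate: (1 + k² − 2rk) − (1 − r²) = (k − r)², never negative. Apart from one degree of freedom, the covariate analysis is never less precise than either.

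**Example, r = 0.3 and k = 1.** The raw standard error is 2.22 × √(2/47) = 0.458. The change factor is 1 + 1 − 0.6 = 1.40, so its standard error is 0.458 × √1.40 = 0.542. The covariate factor is 0.91, giving 0.437. Power for 1.5 points is 90%, 78% and 92.5% respectively.

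**Power for 1.5 points, SD 2.22, 47 v 47 (noncentral t).**

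| Analysis | r = 0.1 | 0.2 | 0.3 | 0.5 | 0.6 |
|---|---|---|---|---|---|
| Raw | 90% | 90% | 90% | 90% | 90% |
| Covariate | 90% | 91% | 92.5% | 96% | 98% |
| Change, k = 0.5 | 86% | 89% | 91% | 96% | 98% |
| Change, k = 0.75 | 78% | 82% | 87% | 95% | 98% |
| Change, k = 1 | 68% | 73% | 78% | 90% | 95% |
| Change, k = 1.25 | 57% | 62% | 67% | 81% | 88% |

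For 3 points at this SD, raw and covariate power exceed 99.9%, and change is at least 98.9% throughout.

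**Other SDs, r = 0.2, k = 1 (raw, covariate, change).**
- 1.5 points, SD 1.98: 95%, 96%, 82%.
- 1.5 points, SD 4.04: 43%, 44%, 29%.
- 3 points, SD 4.04: 94.5%, 95%, 80%.

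**If either VAS test could count as success.** With no effect, the raw and change statistics correlate at (1 − rk)/√(1 + k² − 2rk). At r = 0.3 and k = 1 this is 0.7/1.183 = 0.59, and the chance that at least one is significant is 8.8%. Over the grid it is about 7 to 10%, for one contrast at one time.

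**The case against.** The strongest reply is that an unadjusted comparison in a randomised trial is not an error. That stands. A reader might infer that the treatment estimates are biased or invalid; nothing in the documents supports this. The gain over raw VAS is also small where r is low: at most about 2.5 power points at r of 0.3 or less. Larger gains need r near 0.5 or more, and the documents give no correlation for any outcome.

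A reader might also infer that the plan has two competing primary VAS tests and an inflated error rate. The text does not establish that. The parenthesis may mark change as supportive, or mean changes derived from the one fitted model. A change score is zero for everyone at baseline, so it fits poorly as a response in a model that lists baseline as a time. The sample-size text speaks of a VAS mean difference, which leans towards raw. The 7 to 10% is therefore conditional on a reading that the plan leaves open, not a property of the plan.

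Nor is it right that baseline is never used: a change score is a crude correction. The power figures assume 47 v 47. The model text labels treatment only as dexamethasone or control; if the two dose arms were pooled (94 v 47), raw power for 1.5 points at SD 2.22 would be about 96%.

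Finally, the plan says "The model-based means are unbiased with unbalanced and missing data, so long as the missing data are non-informative (missing at random"). When missingness depends on observed values, the means also need the right covariance model, and robust standard errors do not repair them. Bias from compound symmetry is possible but not shown: the documents give no dropout rate and no covariance.

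**Conclusion.** The point holds as a matter of precision. With complete data, the planned contrasts for raw VAS, ROM, SF-12, KOOS, Jr. and glucose are unadjusted arm differences. A between-arm test of VAS change would be less precise than raw whenever r < k/2. For the 1.5-point VAS contrast the loss against a covariate analysis runs from almost nothing at r = 0.1 to about 8 power points at r = 0.6 (98% against 90%). For the 3-point contrast at SD 2.22 it is negligible. The variance gain is larger for any outcome with a higher baseline correlation. These sizes rest on assumed SD, r and k; the ordering of the variances does not.

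Separately, the role of VAS change from baseline is an ambiguity to clear up. This is a free or cheap improvement, modest for the primary outcome.

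**What to change.** For each of these outcomes, model the post-baseline values with arm by time and with the baseline value as a covariate interacting with time. Compare arms on the adjusted means at each time point. For VAS, name this as the deciding form of the analysis and make the change score descriptive. With the covariate in the model, raw and change VAS give the same treatment contrast, so that choice disappears. It does not settle which time point or which arm pair decides; those remain open.

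The alternative of keeping baseline as a response with a common mean across arms should not be paired with compound symmetry, because baseline is then weighted by the fitted common correlation. At r = 0.2, k = 1 and a fitted correlation of 0.5, the variance factor is 1 + 0.25 − 0.20 = 1.05, against 1 − 0.04 = 0.96 for the covariate. The complete-data covariate contrasts do not depend on the covariance form.

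The cost is a few lines of SAS code and analysis text, with no new data. There are three downsides. The within-arm linear trend test needs the planned model run separately. One degree of freedom is spent per time. Patients without a baseline value need a simple prespecified rule, so that they are not dropped.

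An unstructured covariance, a defined in-hospital summary value and a rewording of the missing-at-random sentence are separate, optional matters with no shown effect; this fix does not need them.
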